6.2 Description of Evaluations

Pilot study evaluations will consist of: 1) assessing baseline eligibility criteria; 2) assessing the intervention for feasibility and acceptability; 3) assessing outcomes of the future pragmatic trial for measurement feasibility; and 4) assessing intervention fidelity.

Definitions of the data elements and sources are itemized below. Unless otherwise mentioned, all data at JHCP will be extracted from the EHR. All data at KPCO will be extracted from the KPCO Virtual Data Warehouse, a quality controlled, common data model that includes data from multiple KPCO data sources covering enrollment, utilization, pharmacy, demographics, mortality, problem list diagnoses, and social history, among other domains.³⁶

Inclusion/ exclusion criteria: As previously described (section 4.1). Data elements will include age, diagnosis codes, current medications on the date of enrollment (see definition "chronic medication count" below). Chronic diagnoses will be from a list of 86 chronic conditions itemized in the Multiple Chronic Conditions Chartbook.³⁷ We have developed a method of counting chronic medications that uses a consensus-based list of Generic Product Index (GPI) categories to be included for polypharmacy estimates.

Patient demographics and diagnoses: Age, gender, and race/ethnicity will be collected from the EHR. ICD-10 codes will be used to identify diagnoses from visit billing codes, hospital and emergency department claims diagnoses, and problem list diagnoses.

Care partner demographics: Age, gender, race/ethnicity, relationship to patient, and health literacy ("How confident are you filling out medical forms by yourself?") will be asked by the project assistant during the scheduling phone call.

Chronic medication count: We will use the approach refined in Optimize to define chronic medication use as any prescription medication for which the patient had at least a 28-day supply on the assessment date.³² We selected a 28-day supply (rather than a supply for a longer time period) because some medications (such as opioid medications) are mostly dispensed in 28-day supplies. Chronic medications exclude the following domains identified by 2-digit GPI codes: vaccines, toxoids, allergenic extracts, oxytocics, local anesthetics—parenteral, general anesthetics, antiseptics and disinfectants, antidotes, diagnostic products, chemicals, and medical

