7.2 Methods and Timing for Assessing, Recording, and Analyzing Safety Parameters

Throughout the study period any physician, pharmacist or health care staff member will be able to report concerns about a safety issue that arises via a dedicated, monitored study email address and phone number as well as via contacting the PIs at each site ([name] at Johns Hopkins; [name] at KPCO). In addition, during the pilot study, study staff will review medical records of all patient participants who have ED visits, hospitalizations, or observation admissions to assess whether any emergency services were likely to have resulted from medication discontinuation. We will also assess whether emergency services were likely to have resulted from adverse effects of non-discontinued medications. Information on use of emergency services will inform the development of safety procedures for the future pragmatic trial.

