7.3 Adverse Events and Serious Adverse Events

We define adverse events as any new negative diagnosis or symptom during the study period that results in seeking medical care. Serious adverse events will be those requiring the use of emergency hospital services. In the ADRD-MCC population we anticipate a baseline hospitalization rate of approximately 30% due to morbidity burden. As described above, we will review medical records of all patients who use emergency hospital services during the pilot study period and use this information to inform adverse event monitoring for the future pragmatic trial. Each month, project assistants will also review the list of enrolled patients who have received intervention materials for any uses of hospital emergency services. These cases will be targeted for record review by the site PI.

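### Section 7 names death neither as a serious adverse event nor as a trigger for review, and sections 7.2 and 7.3 describe different sets of reviewable events

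*Combined protocol and SAP*

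**What the plan says.** Section 7.3 starts from a broad definition of an adverse event that depends on care being sought: "We define adverse events as any new negative diagnosis or symptom during the study period that results in seeking medical care". Its only test of seriousness is then: "Serious adverse events will be those requiring the use of emergency hospital services".

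Two active searches are described.

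- **Section 7.2, record review.** Staff will look at the records of all "patient participants who have ED visits, hospitalizations, or observation admissions", to judge whether stopped or continued medications were the likely cause. No frequency is given.
- **Section 7.3, monthly review.** "Each month, project assistants will also review the list of enrolled patients who have received intervention materials for any uses of hospital emergency services". Cases found this way go to the site PI for record review.

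Section 7.3 also points back to the first search, but in narrower terms: "As described above, we will review medical records of all patients who use emergency hospital services during the pilot study period".

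There are two passive routes. Section 7.2 says that "any physician, pharmacist or health care staff member will be able to report concerns about a safety issue", and section 7.3.1 asks pharmacists and PCPs to report adverse events that they believe the trial caused. Section 7.3.2 follows hospitalizations until discharge and takes reported concerns to the Safety Officer and the IRB.

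Mortality appears only in section 6.2, as one of the KPCO data warehouse domains: "enrollment, utilization, pharmacy, demographics, mortality, problem list diagnoses, and social history". The safety section does not use it, and no equivalent source is named for JHCP.

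**The concern.** Section 7.1 itself recognises that patients or care partners might stop a necessary medication inadvertently, and that agreed discontinuation can bring recurrent symptoms or withdrawal events. The gravest possible consequence is death, and the serious-event rule does not contain it. A patient who dies at home is counted as serious only if emergency hospital care was used on the way.

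This matters because oversight rests on case-finding. There are no stopping rules (section 9.3), a waiver of consent is requested for the intervention and the EHR data (section 11.2), and the Safety Officer discusses the concerns that are brought forward (section 7.3.2). An event that no active search looks for may not reach that discussion. Voluntary reporting is a weak substitute. Someone must hear of the death and, under section 7.3.1, attribute it to the trial. Pharmacists and PCPs are also unmasked, and the delayed group has no pharmacist visit for about 3 months, so reporting could differ between arms.

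The second problem is one of consistency. Sections 7.2 and 7.3 use different lists, so two sites could classify the same non-emergency admission differently.

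**Working it through.** **Step 1. Apply the written rules to each type of event.** The adverse-event column assumes a new diagnosis or symptom.

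| Event | Adverse event (7.3) | SAE (7.3) | Record review (7.2) | Monthly review (7.3) |
|---|---|---|---|---|
| Emergency department visit | Yes | Yes | Yes | Yes |
| Direct admission or observation stay, not through the emergency department | Yes | Unclear; no if read literally | Yes | Unclear; no if read literally |
| Death outside hospital, after outpatient care only | Yes, for the symptom that led to care | No | No | No |
| Death outside hospital, no care sought | No | No | No | No |

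The last two rows are the gap. In the last row the death fails even the parent definition, because no care was sought.

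**Step 2. Does the cross-reference change the table?** Section 7.3 describes the section 7.2 review as covering users of emergency hospital services. The term may therefore be loose shorthand for the three encounter types in 7.2. The anticipated hospitalization rate of about 30%, given straight after the SAE definition, and the follow-up of hospitalizations in 7.3.2 point the same way. On that reading, the second row becomes yes throughout. The last two rows do not change, because no encounter on either list has occurred.

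**Step 3. How many deaths could be involved?** The plan gives no figure to reproduce. The 30% hospitalization rate has no stated period and says nothing about deaths.

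Inputs:

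- N = 60 patients (Précis and section 3)
- t = 3 months = 0.25 year on study (Précis)
- m = annual mortality, **assumed** to lie between 0.05 and 0.20

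Expected deaths = N × [1 − (1 − m)^t]

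- m = 0.05: 60 × (1 − 0.95^0.25) = 60 × 0.01274 = 0.76, about 0.8
- m = 0.20: 60 × (1 − 0.80^0.25) = 60 × 0.05426 = 3.26, about 3.3

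This counts every death in both arms. Those preceded by an emergency visit or an admission would reach at least one of the two reviews. The share that would not is unknown, so for any given m the result is an upper bound on deaths outside both active reviews.

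**The case against.** The strongest reply concerns admissions. A reader of section 7.3 alone might infer that direct admissions escape review altogether. The documents do not support that: section 7.2 commits staff to review every participant with a hospitalization or observation admission, 7.3 refers back to that review, and 7.3.2 follows hospitalizations to discharge. This objection stands, and what is left on admissions is a mismatch of scope between two sections.

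A reader might also infer that every out-of-hospital death would be missed. That goes too far. Staff have a monitored reporting route, pharmacists and PCPs are asked to report, and several planned contacts could reveal a death: the pharmacist's second call, the reminder call in the delayed group, and the 3-month FCMAHS contact for care partners who opted in. None of these is systematic ascertainment of death, so the fair statement is that neither active review would find it.

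The figure of 0.8 to 3.3 could be misread as a count of missed deaths, or of deaths following a medication change. It is neither. It covers all deaths in both arms, although the delayed group's pharmacist component falls at 3–4 months, essentially after the study window. The assumed range also makes no allowance for the exclusion of hospice and long-term-care residents.

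Nor do the documents commit the later ePCT to this SAE definition. They say that information on emergency service use, and from the record reviews, will inform its safety procedures.

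Finally, this is presented as a minimal-risk feasibility pilot, and no endpoint or analysis depends on SAE counts. That is true and limits the statistical consequence. It does not explain why death is left out of the serious-event rule.

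**Conclusion.** The point holds on death. Section 7 names it neither as a seriousness criterion nor as a review trigger. A death outside hospital without emergency hospital care is not an SAE under the written rule and is found by neither active review. This follows from the text and does not depend on any mortality assumption.

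On direct and observation admissions the point is narrower: they are reviewed under 7.2, but 7.3 leaves their SAE status, monthly listing and route to the site PI unclear.

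The size is uncertain. At an assumed annual mortality of 5% to 20%, at most about 0.8 to 3.3 deaths would be expected outside both reviews, and the true number depends on an unknown share that occur without hospital contact. No efficacy or feasibility analysis changes. The change is worth making before enrollment proceeds, because the present rule does not class the gravest outcome as serious in a study that can lead to stopped medications.

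**What to change.** 1. In section 7.3, add death from any cause to the definition of a serious adverse event, and state that it counts whether or not care was sought.
2. Use one list of events in sections 7.2 and 7.3: death, hospitalization, observation admission and emergency department visit. Apply it to SAE status, the record review, the monthly review and referral to the site PI.
3. Add a vital-status check to the monthly review. At KPCO, use the mortality domain named in section 6.2, and confirm its availability, since the shorter list of domains in section 10.2 omits it. At JHCP, the sponsor needs to name a source, because the documents give none.

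The cost is protocol wording, a small addition to a monthly task that project assistants already have, and more events classed as serious. The documents do not describe an automated monthly data extract, so the effort at each site should be confirmed. Treatment, sample size and analysis are unaffected.

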7.3.1 Reporting Procedures

We will provide contact information for the JHU and KPCO Project Managers (TBD) and the JHU and KPCO PIs ([name] and [name]) to all clinical pharmacists and PCPs at the pilot study sites and ask them to report any perceived adverse events resulting from the trial.

7.3.2 Follow-up for Adverse Events

For each report, the JHU and KPCO PI will contact the clinical pharmacist and/or PCP to review the potential concern. All potential concerns will be noted and discussed with the Safety Officer as part of reviewing pilot study results and will be reported to the IRB. Duration of follow-up will extend until discharge from the hospital for hospitalizations or completion of any acute care services associated with an adverse event.

7.4 Safety Monitoring

An independent Safety Officer will be appointed to serve as the data safety monitor.

8 INTERVENTION DISCONTINUATION

For this pilot study of a pragmatic intervention, we do not have intervention discontinuation criteria.

9 STATISTICAL CONSIDERATIONS

9.1 General Design Issues

This is a pilot of a future pragmatic, cluster randomized trial. The pilot aims to assess feasibility and acceptability of the intervention. There are no statistical hypotheses. Our conceptual hypotheses are that the pilot intervention will be acceptable to patients and clinicians and feasible to conduct. In Aims 1 and 2a, our focus will be on descriptive statistics (counts and proportions). In Aim 2b, the primary analyses will rely on intention-to-treat analysis to present the comparative results of the trial. All events following randomization will be counted. Analyses using post-randomization data (eg, intervention compliance) will be discussed as secondary analyses. We will distinguish non-compliance with intervention from non-compliance with follow-up (ie, missing data).

For our primary outcome measure, pMRCI, we will first perform correlation analyses between chronic medication count and pMRCI scores at baseline. We will analyze changes in pMRCI before and after intervention and evaluate the impact of intervention assignment on the change scores using linear regression. The cluster by health system effect will be accounted for in the calculation of robust standard errors. Given the pilot nature of this trial, we will focus on estimates of precision in detecting treatment effects that will aid in the planning of a larger, sufficiently powered ePCT. We will also explore treatment effects by gender, age strata and race/ethnicity, again focusing on estimates of with-stratum variabilities instead of statistical significance. We will use multiple imputation to account for missing data.

For our secondary outcome measure, FCMAHS, we will first construct summary scores of the FCMAHS subscales using principal components analysis. We will then analyze changes in FCMAHS before and after intervention and evaluate the impact of intervention assignment on the change scores using linear regression.

9.2 Sample Size and Randomization

Sample size calculation: With an attrition rate of 10%, a sample size of 30 dyads per arm will produce a 2-sided 95% confidence interval with a width equal to 0.4 standard deviation (SD) when the SD of the study outcome (ie, based on normalized score) is 1.

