The eligible patient population for the pilot study will be all patients at the two pilot clinics who are age 65 or greater with a diagnosis of Alzheimer's disease and related dementias (ADRD) from either ICD visit codes or documentation on the problem list. Patients must also be taking 5 or more chronic medications, and active patients, defined as having ≥ 1 visit to the primary care clinic within the past year. We will enroll 60 patient-care partner dyads (15 dyads per arm at each site).

STUDY TEAM ROSTER

Principal Investigator:	[name], MPH, PhD Johns Hopkins University School of Medicine [name] [contact] [contact] [contact]
Co-Investigators:	[name], MS Institute for Health Research, Kaiser Permanente Colorado [name] [contact] [contact] [contact] Site Principal Investigator, Kaiser Permanente
	[name], MPH Johns Hopkins University School of Medicine [name] [contact] [contact] [contact] Co-Investigator
	[name] Johns Hopkins Bloomberg School of Public Health [name] [contact] [contact] [contact] Co-Investigator
	[name] Johns Hopkins Center on Aging and Health [name] [contact] [contact] [contact] Co-Investigator, Statistician
	[name], MSPH Institute for Health Research, Kaiser Permanente Colorado

[name] [contact] [contact] [contact] Co-Investigator

PARTICIPATING STUDY SITES

[name], MPH, PhD

Johns Hopkins University School of Medicine [name] [contact] [contact] [contact]

[name], MS

Institute for Health Research, Kaiser Permanente Colorado [name] [contact] [contact] [contact]

1 STUDY OBJECTIVES

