6.2.1 Screening Evaluation Consenting Procedure

As described in section 4.3, initial eligibility will be determined based on available clinical and claims data under a waiver of HIPAA Authorization.

Project assistants will serve as scheduling coordinators for the pilot study. Dyads who do not opt out (and those who opt in) will be called by the project assistant approximately 14 days after the study materials are mailed. Using the same approach that clinic staff use to call patients with dementia on the phone and identify their care partners during the course of clinical care, the project assistant will use an IRB-approved script (attached) to describe the pharmacist consult and assess interest. If the patient declines to identify a care partner and does not have a care partner listed in the EHR, the dyad will not be eligible. This phone call is described in section 4.3.

Participation in the pharmacist consult is not contingent on completion of the secondary outcome measure, FCMAHS. After scheduling the pharmacist consult, project assistants will offer care partners the option of completing the FCMAHS. They will obtain verbal consent for the FCMAHS when administering it over the phone (see script). If the care partner cannot complete the FCMAHS over the phone during the scheduling phone call,

the project assistant will offer to call back before the pharmacist visit (up to 28 days) or to later e-mail them a link to an electronic version.

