6.2.3 Follow-up Visits

As described in the Evaluations Table, dates for follow up measurements will be relative to baseline/enrollment. This is defined as the date of the enrollment phone call. Data will be extracted from the EHR and VDW as described above. There will be one follow up call/e-mail to administer the FCMAHS 3 months after enrollment for care partners who have opted to complete it.

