6.2.4 Completion/Final Evaluation

As described above, there will be one follow up phone call/e-mail to administer the FCMAHS 3 months after enrollment. Care partners who do not wish to complete the FCMAHS by phone will be offered an electronic version and will be e-mailed a link. All

other data will be extracted from the EHR and VDW. If participants discontinue the intervention early (eg, by opting out during the pharmacist phone call), we will still extract their data from the EHR and VDW but will not offer the FCMAHS.

7 SAFETY ASSESSMENTS

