9.5 Data Analyses

In Aims 1 and 2a, our focus will be on descriptive statistics (counts and proportions). In Aim 2b, the primary analyses will rely on intention-to-treat analysis to present the comparative results of the trial. All events following randomization will be counted. Analyses using post-randomization data (eg, intervention compliance) will be discussed as secondary analyses. We will distinguish non-compliance with intervention from non-compliance with follow-up (ie, missing data).

For our primary outcome measure, pMRCI, we will first perform correlation analyses between chronic medication count and pMRCI scores at baseline. We will analyze changes in pMRCI before and after intervention and evaluate the impact of intervention assignment on the change scores using linear regression. The cluster by health system effect will be accounted for in the calculation of robust standard errors. Given the pilot nature of this trial, we will focus on estimates of precision in detecting treatment effects that will aid in the planning of a larger, sufficiently powered ePCT. We will also explore treatment effects by gender, age strata and race/ethnicity, again focusing on estimates of with-stratum variabilities instead of statistical significance. We will use multiple imputation to account for missing data.

For our secondary outcome measure, FCMAHS, we will first construct summary scores of the FCMAHS subscales using principal components analysis. We will then analyze changes in FCMAHS before and after intervention and evaluate the impact of intervention assignment on the change scores using linear regression.

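### The 0.4 SD precision in section 9.2 is a one-arm half-width; the Aim 2b between-arm comparison of FCMAHS has a half-width of about 0.55 SD at best, and wider if uptake of the optional questionnaire is low

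*Combined protocol and SAP*

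**What the plan says.** Section 9.2 justifies the sample size by precision: "With an attrition rate of 10%, a sample size of 30 dyads per arm will produce a 2-sided 95% confidence interval", which it then describes as "with a width equal to 0.4 standard deviation (SD", "when the SD of the study outcome (ie, based on normalized score) is 1". It does not name the outcome. It does not say whether the width is full or half, or whether the interval is for one arm or for the difference between arms. The 10% is not defined further.

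Sections 9.1 and 9.5 say what will be estimated. On FCMAHS: "In Aim 2b, the primary analyses will rely on intention-to-treat analysis to present the comparative results of the trial", with change scores regressed on assignment. pMRCI, called the primary outcome measure, also gets a regression of change on assignment.

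FCMAHS is collected differently from the record-based outcomes:

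- Section 6.2.1: "Participation in the pharmacist consult is not contingent on completion of the secondary outcome measure, FCMAHS". Sections 4.3 and 11.2 add that it is offered after the consult has been scheduled and needs its own verbal consent.
- Section 6.2.3: "There will be one follow up call/e-mail to administer the FCMAHS 3 months after enrollment for care partners who have opted to complete it".
- Section 6.2.4, on participants who stop the intervention early: "we will still extract their data from the EHR and VDW but will not offer the FCMAHS".

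Sections 6.2.2 and 9.2.1 place randomization before the scheduling call, and 6.2.2 dates enrolment to that call. A dyad can therefore be among the 30 in its arm with no FCMAHS at all.

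**The concern.** The plan offers one precision figure as if it served the whole study. Two features of the FCMAHS comparison make that figure too favourable for Aim 2b. First, the estimate is a difference between two arms, which is less precise than one arm's mean. Second, a change score needs both administrations of a questionnaire that care partners are free to decline, whereas the only loss shown in 9.2 is 10%.

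Precision is the plan's only justification for its sample size, and the stated purpose of the pilot is to inform a larger trial. A reader who takes 0.4 SD as the precision of the FCMAHS treatment effect would expect a better estimate than the design can give.

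**Working it through.** **Inputs.** Section 9.2: 30 dyads per arm, 10% attrition, two-sided 95% interval, SD = 1, width 0.4. Evaluable n = 30 × 0.9 = 27 per arm. FCMAHS uptake and completion: not given, so assumed below. Dyads are treated as independent with equal SD in both arms.

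**Step 1: reproduce the plan's figure.** The half-width of one arm's mean is t(0.975, n−1)/√n.

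- n = 27: 0.396 SD.
- n = 26: 0.404 SD.

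So 27 is the smallest n with a half-width of 0.40 or less, and 27/0.9 = 30. This matches 9.2 exactly. Other readings at 27 per arm do not give 0.4:

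| Reading | Value (SD) |
|---|---|
| One arm, full width (t) | 0.791 |
| One arm, half-width (normal quantile) | 0.377; reaching 0.4 would need 25 evaluable, 28 enrolled |
| Between-arm difference, half-width (t) | 0.546 |
| Between-arm difference, full width (t) | 1.092 |
| Both arms pooled (54), half-width / full width (t) | 0.273 / 0.546 |

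**Step 2: the quantity Aim 2b estimates.** The half-width of the difference is t(0.975, 2n−2) × √(2/n). At n = 27 this is 0.546 SD, and 0.546/0.4 = 1.365, so it is more than a third larger than the stated figure with no FCMAHS non-uptake at all. A between-arm half-width of 0.4 would take 50 evaluable per arm (50/0.9, rounded up: 56 randomized).

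**Step 3: allow for FCMAHS non-completion.** The 10% can be read in two ways. n is rounded down.

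(a) The 10% is meant to cover every reason for lacking a two-time-point FCMAHS. Then n = 30 × net completion:

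| Net completion (assumed) | n per arm | Between-arm half-width (SD) | Relative to 0.546 |
|---|---|---|---|
| 90% | 27 | 0.546 | 1.00 |
| 80% | 24 | 0.581 | 1.06 |
| 70% | 21 | 0.624 | 1.14 |

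(b) The 10% is loss after baseline, on top of non-uptake. Then n = 30 × uptake × 0.9:

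| Uptake (assumed) | n per arm | Between-arm half-width (SD) | Relative to 0.546 |
|---|---|---|---|
| 100% | 27 | 0.546 | 1.00 |
| 90% | 24 | 0.581 | 1.06 |
| 70% | 18 | 0.677 | 1.24 |
| 50% | 13 | 0.810 | 1.48 |

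**The case against.** The strongest reply is that 9.2 is not about FCMAHS. The documents call pMRCI primary and FCMAHS secondary. The sentence about focusing on precision sits in the pMRCI paragraph, and pMRCI also has a between-arm regression. Sizing on the primary outcome alone is ordinary practice. Much of this stands. A reader might infer that 9.2 sets an N for FCMAHS and assumes every care partner takes it. The documents do not support that: 9.2 names no outcome, and the undefined 10% may cover all non-completion, in which case 90% net completion leaves 27 per arm and nothing further is lost. But if 9.2 concerns pMRCI only, the Aim 2b comparison has no precision statement, and the same edit is needed.

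A reader might also infer that 0.4 SD is secure for the record-based outcomes and fails only for FCMAHS. That is not supported either. The between-arm half-width for pMRCI at 27 per arm is the same 0.546 SD. Availability of pMRCI data is itself an Aim 2a unknown, and dyads can be lost at the scheduling call after randomization (section 4.3).

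Nor is there an arithmetic slip: 30 × 0.9 = 27 and the 0.396 both check.

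Two further points limit the consequence. The plan supports uptake with telephone administration, a call-back of up to 28 days and an e-mailed link. It has no statistical hypotheses or decision rule that uses 0.4, and planners of the later trial will have the realised interval and response rate. Multiple imputation does not answer the point: it appears in the pMRCI paragraph, the FCMAHS paragraph names no missing-data method, and imputation cannot generally restore information from care partners who were never measured.

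**Conclusion.** The concern holds in a limited form. The 0.4 SD in section 9.2 is correct as the half-width of one arm's mean at 27 evaluable dyads, but it is not the precision of the Aim 2b between-arm comparison. That half-width is about 0.55 SD at 27 per arm, which follows from the plan's own inputs with SD = 1.

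The additional widening from FCMAHS non-completion is conditional. It occurs if net two-time-point completion is below 90%, and its size cannot be fixed because the response rate is something the pilot sets out to measure. Over the assumed values the half-width runs from 0.58 SD (80% net) to 0.81 SD (50% uptake followed by 10% attrition). This is a matter of stating precision correctly; it does not invalidate the pilot's sample size.

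**What to change.** In section 9.2:

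- Label 0.4 SD as the half-width of a one-arm mean at 27 evaluable dyads.
- Say what the 10% covers, and whether it includes care partners who decline FCMAHS.
- Give the between-arm half-width on the same scale for every outcome: about 0.55 SD at 27 per arm, for pMRCI and chronic medication count as well as FCMAHS. Setting a one-arm 0.4 for some outcomes beside between-arm figures for FCMAHS would mix two quantities and exaggerate the contrast.
- Give FCMAHS between-arm precision over a stated range of completion rates, marked as assumptions, using whichever table above matches the definition chosen for the 10%.

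In section 9.5, say that the Aim 2b comparison is read at that precision.

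The cost is a few sentences and a less favourable stated precision. No change in enrolment or data collection is needed.

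### Section 9.2 labels a half-width as a width: with 27 evaluable dyads per arm, 0.4 SD is the half-width for one arm's mean (full width 0.79 SD), and no precision is given for the between-arm difference (±0.55 SD if SD = 1 is the change-score SD)

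*Combined protocol and SAP*

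**What the plan says.** Section 9.2 (Sample Size and Randomization) contains the only sample-size justification. It takes 30 dyads in each arm, allows for 10% attrition, sets the normalized outcome's SD to 1, and concludes that this design "will produce a 2-sided 95% confidence interval with a width equal to 0.4 standard deviation (SD"). It does not say whether the interval is for one arm's mean or for the difference between arms. It also does not say whether the SD of 1 belongs to a score at one time point or to a change score.

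The Précis (Sample Size and Population) gives the same total: "We will enroll 60 patient-care partner dyads (15 dyads per arm at each site").

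Sections 9.1 and 9.5 describe the analysis. For the pMRCI and again for the FCMAHS, the plan will "evaluate the impact of intervention assignment on the change scores using linear regression". In the pMRCI paragraph it adds that, because this is a pilot, "we will focus on estimates of precision in detecting treatment effects" to help plan the larger trial. Section 9.1 also says that there are no statistical hypotheses.

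**The concern.** No power calculation is given, so the interval width is the whole quantitative basis for 60 dyads. Read literally, a width of 0.4 SD means an estimate known to within ±0.2 SD. That is implausibly tight for about 27 observations with SD 1: the standard error of one mean is already 1/√27 = 0.19.

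The planned analysis is also comparative, and a difference between two arms is less precise than either arm's mean. A reader planning the larger trial from Section 9.2 could therefore expect considerably more from the pilot's outcome data than it can give. The FCMAHS may fare worse, because completing it is optional (Section 6.2.1: "Participation in the pharmacist consult is not contingent on completion of the secondary outcome measure, FCMAHS").

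**Working it through.** **Inputs (Section 9.2).** 30 dyads per arm; 10% attrition; two-sided 95% interval; SD = 1. Evaluable dyads per arm: 30 × 0.9 = 27 (derived, not stated).

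**Reproducing the plan's 0.4.** For one arm's mean:

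- half-width = t(0.975, 26)/√27 = 2.056/5.196 = **0.396**
- full width = 2 × 0.396 = **0.791**

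So 0.4 comes back as a half-width. The fit is close: n = 26 gives 0.404, n = 27 is the smallest sample with a half-width of 0.40 or less, and 27/0.9 is exactly 30.

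**Looking for any reading in which 0.4 is a full width (SD = 1).**

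| Quantity | Half-width (t) | Full width (t) | Full width (z) |
|---|---|---|---|
| One arm, n = 27 | 0.396 | 0.791 | 0.754 |
| One arm, n = 30 (no attrition) | 0.373 | 0.747 | 0.716 |
| Both arms pooled, n = 54 | 0.273 | 0.546 | 0.533 |
| Both arms pooled, n = 60 | 0.258 | 0.517 | 0.506 |
| Difference, 27 per arm | 0.546 | 1.092 | 1.067 |
| Difference, 30 per arm | 0.517 | 1.034 | 1.012 |

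None gives 0.4. The smallest full width is 0.506.

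**The between-arm difference (27 per arm).**

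- half-width = t(0.975, 52) × √(2/27) = 2.007 × 0.272 = **0.546**
- full width = **1.092**

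For the difference, 0.4 is therefore neither the width nor the half-width.

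**If SD = 1 is the SD at one time point.** The change score then has SD = √(2(1 − r)), where r is the baseline-to-3-month correlation. The documents give no r. Solving for the change SD and then r = 1 − SD²/2:

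- one-arm full width 0.4: SD = 0.2/0.396 = 0.506 (unrounded inputs), r ≈ 0.87
- difference, full width 0.4: SD = 0.2/0.546 = 0.366, r ≈ 0.93
- difference, half-width 0.4: SD = 0.4/0.546 = 0.732, r ≈ 0.73

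Over an assumed range of r, the half-width for the difference is 0.65 at r = 0.3, 0.55 at 0.5, 0.42 at 0.7 and 0.24 at 0.9.

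**Sample sizes that would match the literal text (t-based, SD = 1), for scale only.**

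- one mean, full width 0.4: 99 evaluable; 99/0.9 = 110 enrolled
- difference, full width 0.4: 194 evaluable per arm; 194/0.9 = 215.6, so 216 enrolled per arm
- difference, half-width 0.4: 50 evaluable per arm; 50/0.9 = 55.6, so 56 enrolled per arm

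**FCMAHS.** The documents give no completion rate. Assuming 21 to 15 completers per arm, the half-width for the difference is t(0.975, 40) × √(2/21) = 2.021 × 0.309 = 0.62, rising to t(0.975, 28) × √(2/15) = 2.048 × 0.365 = 0.75.

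**The case against.** The best defence is that this is a wording slip. The 0.4, the attrition allowance and the 30 per arm all agree once the word for width is read as margin of error, so no calculation failed. Little rests on the figure: the primary objective is feasibility and acceptability, there are no hypotheses, and no interim analysis or stopping rule uses it. The precision that Sections 9.1 and 9.5 want to carry forward can be read as the variability seen in the data rather than the advance figure. Section 9.2 also never claims 0.4 for the treatment difference. Finally, 0.55 is conditional: it comes from a simple two-sample interval, whereas the plan uses robust standard errors for health system and multiple imputation. The 10% loss may be pessimistic for the pMRCI, because Section 6.2.4 keeps extracting record data after early discontinuation.

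Much of this stands. The slip is probably one of labelling, 30 per arm is not itself an error, and the missing figure for the difference is an omission rather than a miscalculation. The defence does not rescue the sentence. It says width, and nothing elsewhere in the documents corrects it. Even on the generous reading, 0.4 describes one arm's mean and not the treatment effect that the analysis sections emphasise. Dropping attrition altogether moves the half-width for the difference only from 0.55 to 0.52. The FCMAHS range is illustrative and should be labelled so.

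**Conclusion.** The concern holds: Section 9.2 is wrong as written. On its own inputs the full width for one arm's mean is 0.79 SD, not 0.40 SD, a factor of 2.0. That the authors meant a half-width is an inference, though it is the standard reading that returns their number. That 0.4 is not the full width is arithmetic.

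The precision of the between-arm difference is not stated. It is ±0.55 SD (full width 1.09 SD), so a reader who applied the stated width to the treatment effect would be out by 1.09/0.40 ≈ 2.7. The difference figures assume that SD = 1 refers to the analysed change score, 27 evaluable dyads per arm, no baseline adjustment, and no allowance for clustering or imputation. If SD = 1 is a single-time-point SD, they depend on a correlation that the plan would have to state.

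This should be fixed, but it is a reporting and planning error. It does not undermine the pilot's feasibility aims, type I error or participant safety, and it gives no reason to change the sample size.

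**What to change.** Keep 60 dyads and replace the sentence in Section 9.2 with text along these lines:

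> Allowing for 10% attrition, 27 evaluable dyads per arm give a two-sided 95% confidence interval of ±0.40 SD (width 0.79 SD) for a within-arm mean and ±0.55 SD (width 1.09 SD) for the between-arm difference, where 1 is the SD of the analysed change score and clustering is ignored. FCMAHS intervals will be wider if fewer care partners complete it, because width scales approximately with 1/√(number of completers); for example, ±0.62 to ±0.75 SD for the difference if 21 to 15 per arm complete it (assumed, for illustration).

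If SD = 1 was meant as the SD at one time point, say so, state the assumed baseline-to-3-month correlation, and recompute both intervals with change SD = √(2(1 − r)).

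The cost is two sentences and a decision on which SD is meant. No participants are added and no analysis changes. The only downside is that the stated precision looks less favourable.
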